### 1.2.1 Primary estimand(s)

The estimand is the precise description of the treatment effect and reflects strategies to address events occurring during the trial conduct which could impact the interpretation of the trial results (e.g., premature discontinuation of treatment).

The primary clinical question of interest is: will treatment with ofatumumab allow young and very early RRMS patients to achieve NEDA-3 at 18 months?

The justification for the primary estimand is that it will capture the effect of ofatumumab on shutting down MS inflammatory and associated clinical disease activity within the central nervous system (CNS) in a RRMS population that is at first diagnosis.

The primary estimand is described by the following attributes:

- **Population:** Defined through appropriate inclusion/exclusion criteria to reflect the targeted population. Young adult and very early RRMS (defined as within 6 months of diagnosis of clinically definite RRMS) patients that are DMT treatment naïve.
- **Variable:** NEDA-3 (relapse-free, clinical disability progression-free, MRI activity-free) in Months 6 to 18 (yes/no)
- **Treatment of interest:** An initial dose regimen consisting of doses administered at Baseline/Week 0 (Day 1), followed by Week 1 (Day 7), Week 2 (Day 14), and then every month thereafter, beginning at Week 4 (Month 1) until Month 18 (see [Figure 1](#)). All doses of ofatumumab will be given subcutaneously via an auto-injector at a dose of 20 mg. Healthy controls will be used for comparison purposes and will not receive study treatment.
- **Intercurrent event:** Treatment discontinuation due to lack of efficacy or death

- **Summary measure:** Proportion of participants achieving NEDA-3 in Months 6 to 18

### 1.2.2 Secondary estimand(s)

There are no secondary estimands specified for this study.

## 2 Statistical methods

### 2.1 Data analysis general information

The statistical analysis outlined in this SAP will be performed by United BioSource LLC (UBC), a Novartis-designated Contract Research Organization (CRO), using SAS® version 9.4 or higher.

The primary analysis will be based on Month 18 data, i.e., all data up to and including Month 18. This analysis will be performed after all participants have completed their Month 18 visit, discontinued study treatment prior to Month 18 (ofatumumab-treated participants) or discontinued the study prior to Month 18 (healthy control participants) (see [Section 2.1.1](#) and [Section 2.13](#) for additional details). The final analysis will include all data through Month 30.

For continuous variables, descriptive statistics will include number of participants (n) with available data, mean, standard deviation, minimum, maximum, median and 25th and 75th percentiles. For categorical variables, frequency counts and percentages will be reported. Where appropriate, 2-sided 95% confidence intervals (CIs) for point estimates of the mean or proportion will be provided.

In general, data summaries will be presented for ofatumumab-treated participants in the relevant analysis set. In instances where data are collected for both ofatumumab-treated participants and healthy control participants, data summaries will be presented **by Cohort** (ofatumumab-treated participants or healthy control participants) and on all participants in the respective analysis set.

All data (collected or derived) will be listed appropriately.

#### 2.1.1 General definitions

##### Investigational treatment

The investigational treatment (study treatment) will refer to the administration of ofatumumab provided by Novartis in an auto-injector pen containing 20 mg ofatumumab (20 mg/0.4 ml) for subcutaneous administration to participants as per the assessment schedule.

##### Study day 1, study day and event duration

**Study Day 1** is defined as the date of the first dose of ofatumumab for ofatumumab-treated participants and the date of the Week 0 visit for healthy control participants.

For assessment/event dates on or after Study Day 1, the **study day of the assessment/event** will be calculated as follows:

- [(date of assessment/event – date of first dose of ofatumumab) + 1] for ofatumumab-treated participants
- [(date of assessment/event – date of Week 0 visit) + 1] for healthy control participants

For assessment/event dates prior to Study Day 1, the **study day of the assessment/event** will be calculated as follows:

- (date of assessment/event – date of first dose of ofatumumab) for ofatumumab-treated participants
- (date of assessment/event – date of Week 0 visit) for healthy control participants

The **duration of an event** in days will be calculated as follows:

- (event end date – event start date) + 1

## Screening

Screening refers to any procedures (e.g., checking inclusion and exclusion criteria) performed prior to the first dose of ofatumumab for ofatumumab-treated participants or prior to the Week 0 visit for healthy control participants. Per protocol, participant informed consent must be obtained prior to performing any study related activity. The date of signing of informed consent is the start date of the screening period. Any assessment obtained during the screening period will be labelled as a screening assessment.

## Baseline

Unless otherwise specified, baseline will be derived as follows:

- For ofatumumab-treated participants, baseline is the last non-missing assessment, including unscheduled assessments, obtained prior to or on the date of the first dose of ofatumumab.
- For healthy control participants, baseline is the last non-missing assessment, including unscheduled assessments, obtained prior to or on the date of the Week 0 visit.

Unless otherwise specified, all assessments obtained after the date of the first dose of ofatumumab for ofatumumab-treated participants, or after the date of the Week 0 visit for healthy control participants, are considered post-baseline assessments.

## Nominal visits

Nominal visits are defined as all scheduled visits as per the clinical study protocol including the EOS visit. The definition of nominal visit excludes unscheduled visits.

## Month 18 interim analysis data cut-off

As noted in [Section 2.1](#), the primary analysis will be based on Month 18 data (i.e., all data up to and including Month 18) and performed after all participants have completed their Month 18 visit, discontinued study treatment prior to Month 18 (ofatumumab-treated participants) or discontinued the study prior to Month 18 (healthy control participants). The data cut-off for the Month 18 interim analysis is defined for different participant scenarios in [Table 2](#). Note that visits are assumed to be nominal visits.

**Table 2 Month 18 interim analysis data cut-off for different participant scenarios**

Participant scenario	Cut-off	Participant data included in Month 18 interim analysis (primary analysis)
Completed Month 18 visit	Date of Month 18 visit + 7 days (inclusive)	All available data up to the date of the Month 18 visit + 7 days (inclusive)*
Did not complete Month 18 visit		
Discontinued study prior to Month 18 visit	None	All available data
Did not discontinue study prior to Month 18 visit	Date of next scheduled visit after Month 18 (exclusive)	All available data up to the date of the next scheduled visit (including home visit) after Month 18 (exclusive).** If the next scheduled visit after Month 18 has not been completed, all available data is used.

\* Including data such as adverse events, medications, non-drug therapies/procedures, protocol deviations and relapses that started prior to or on the date of the Month 18 visit + 7 days.

\*\* Including data such as adverse events, medications, non-drug therapies/procedures, protocol deviations and relapses that started prior to the date of the next scheduled visit (including home visit) after Month 18.

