8.3.6 Magnetic Resonance Imaging (MRI)

All participants will undergo MRI scanning of the brain, within +/- 7 days of the visit, according to the assessment schedule in Table 8.1.

MRI scans will be read by the central MRI reading center. Prior to the start of the study, the MRI technician from each study site will receive an MRI Manual, outlining the minimum criteria needed for MRI capabilities, technical implementation, image quality requirements and MRI administrative procedures.

The site will be asked to program the MRI scanner that is designated for evaluation of the study participants. Site will be asked to perform and submit a dummy scan (so called “dummy or dry run”) to the central MRI reading center to assess the image quality and to evaluate the compatibility of the electronic data carrier. Once the dummy run has been accepted, all the parameter settings for the study specific MRI sequences must remain unchanged for the duration of the study. Finally, if the site is already pre-approved for performing conventional MRI scan sequences by the imaging vendor, the dummy or dry run may be skipped.

Each MRI scan performed for the study needs to be previewed by a local neuroradiologist. During the study, the quality of each scan performed will be assessed by the central MRI reading center. The MRI scan should be sent to the central MRI reading center upon completion of each individual scan. As soon as the scan is received by the central MRI reading center, it will be evaluated for quality, completeness and adherence to the protocol. Confirmation of MRI quality or a description of the quality problems, if detected, will be communicated to the site. If a scan is incomplete or incorrectly performed, the study center will be asked to repeat it as soon as possible. After completion of the quality check, all scans will be analyzed according to the MRI protocol.

Restrictions to MRI schedule

To avoid interferences caused by steroids (in regard to Gd⁺-enhancing lesions) for the treatment of MS relapse and diagnostic challenges with concomitant participant migraines, the following restrictions apply for this study:

- In case of relapse, if an MRI has been scheduled within 30 days of the initiation of steroid treatment, MRI (with Gd⁺ enhancement) should be performed **before** steroid treatment is initiated.

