 - No MRI should be performed while a participant is on steroid therapy for relapse and within the following 30 days upon termination of steroid treatment.
- 

[REDACTED]

[REDACTED]

[REDACTED]

[REDACTED]

[REDACTED]

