### 2.4.1.1 Visit windows

Visit windows will be used for data that are summarized by visit; they are based on the study evaluation schedule and comprise a set of days around the nominal visit day. When visit windows are used, all visits, including unscheduled visits, will be re-aligned (i.e., they will be mapped into one of the visit windows). In the case of major deviations from the visit schedule, or due to unscheduled visits, several assessments for a participant may fall in a particular visit window (either scheduled or unscheduled). Approaches for handling multiple assessments in a visit window are outlined below.

The following steps are used to determine the cut-offs for post-baseline visit windows:

- The visit window associated with the previous assessment ends prior to the middle point; the visit window associated with the latter assessment begins after the middle point. In case the middle point is an exact study day, it will belong to the previous assessment.
- The visit window of the first post-baseline assessment starts with Study Day 2, unless otherwise indicated.

Tables 3, 4, 5 and 6 provide visit windows for applicable parameters.

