**Table 4 Visit windows for vital signs**

Analysis visit	Nominal time point	Scheduled visit day (target Visit window (study days) study day)	
Baseline/Week 0	BSL/Wk0	1	≤1
60 Minutes Post-Injection*	60 Minutes Post-Injection	1	1 (post-injection)
Week 1	Wk1	7	2 to 10
Week 2	Wk2	14	11 to 21
Week 4	Wk4	28	22 to 59
Month 3	M3	90	60 to 135
Month 6	M6	180	136 to 270
Month 12	M12	360	271 to 450
Month 18	M18	540	451 to cut-off day
Month 30	M30/EOS	900	≥cut-off day + 1

\* Only applicable to ofatumumab-treated participants.

Note:

- Baseline is derived as outlined in [Section 2.1.1](#).
- Cut-off day is the study day of the Month 18 interim analysis data cut-off described in [Section 2.1.1](#).

**Table 5** Visit windows for [REDACTED] /  
hematology and chemistry labs / smoking status

Analysis visit	Nominal time point	Scheduled visit day (target study day)	Visit window (study days)
Baseline/Week 0	BSL/Wk0	1	≤1
Month 18	M18	540	2 to cut-off day
Month 30	M30/EOS	900	≥cut-off day + 1

Note:

- Baseline is derived as outlined in [Section 2.1.1](#).
- Cut-off day is the study day of the Month 18 interim analysis data cut-off described in [Section 2.1.1](#)

**Table 6** Visit windows for MRI

Analysis visit	Nominal time point	Scheduled visit day (target study day)	Visit window (study days)
Baseline/Week 0	BSL/Wk0	1	≤1
Month 6	M6	180	2 to 270
Month 12	M12	360	271 to 450
Month 18	M18	540	451 to cut-off day
Month 30	M30/EOS	900	≥cut-off day + 1

Note:

- Baseline is derived as outlined in [Section 2.1.1](#).
- Cut-off day is the study day of the Month 18 interim analysis data cut-off described in [Section 2.1.1](#).

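### A reading-centre repeat of the Month 18 MRI done more than 7 days after the visit is lost to the primary analysis, because the SAP cut-off makes no provision for it

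*SAP*

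**What the plan says.** **Protocol 8.3.6 (MRI).** Scans are to be done within 7 days either side of the visit, and the central reading centre checks the quality of each one. "If a scan is incomplete or incorrectly performed, the study center will be asked to repeat it as soon as possible". No outer limit is given for the repeat, and the section does not say how a repeat relates to the 7-day window. Separately, no scan is allowed during steroid treatment for a relapse or "within the following 30 days upon termination of steroid treatment". Where a scan is scheduled within 30 days of starting steroids, it "should be performed before steroid treatment is initiated".

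**SAP Table 2.** For participants who completed the Month 18 visit, the primary analysis takes in "All available data up to the date of the Month 18 visit + 7 days (inclusive"). For those still in the study who did not complete that visit, the cut-off is "Date of next scheduled visit after Month 18 (exclusive").

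**SAP 2.4.1.1 and Table 6.** Under visit windowing, "all visits, including unscheduled visits, will be re-aligned" by study day. The general boundary rule is the midpoint between assessments: "The visit window associated with the previous assessment ends prior to the middle point". Table 6, however, gives the Month 18 MRI window as "451 to cut-off day", and Month 30 starts the next day.

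**SAP 2.2, 2.5.3, 2.5.4, 2.5.6 and 5.1.3.3.** A participant who completed the Month 18 visit but has no Month 18 MRI is removed from the mFAS unless disease activity was shown. The supplementary non-response imputation counts the same participant as not achieving NEDA-3.

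**The concern.** The 7 days allowed by Table 2 match the protocol's window for a first scan but leave nothing for the repeat that the protocol itself requests. A first scan done 7 days after the visit and then rejected cannot be repeated in time. The readable SAP text contains no exception.

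The scan at stake helps decide the MRI component of the primary endpoint. Its loss is linked to outcome: participants with activity already shown stay in as failures, activity-free participants leave, and activity visible only on the late scan is not seen. The Month 18 brain-volume change, a secondary comparison with healthy controls, loses values by the same route.

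**Working it through.** **1. The plan's own precision figures.** Inputs from SAP 3.1: n = 100, proportions 80% and 85%, dropout 15%.
- Half-width = 1.96 × √(p(1−p)/n). At 80%: 1.96 × √(0.16/100) = 7.84%. At 85%: 1.96 × √(0.1275/100) = 7.00%.
- Enrolment = 100/0.85 = 117.6, so 118.
- All three reproduce. They use the normal approximation. The planned Clopper-Pearson interval (SAP 2.5.2) has half-widths of 8.3% (80/100) and 7.4% (85/100).

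**2. Where the MRI windows end.** Target days are 180, 360, 540 and 900 (Table 6).
- Midpoints: (180+360)/2 = 270; (360+540)/2 = 450; (540+900)/2 = 720.
- Table 6 uses 270 and 450 for Months 6 and 12, each 90 days past target. By the same rule Month 18 would run to Day 720.
- With the visit on Day 537, 540 or 543 (the ±3 days of protocol Table 8-1), the cut-off falls on Day 544, 547 or 550, and Month 30 begins on Day 545, 548 or 551.
- A participant who missed the Month 18 visit but remains in the study keeps scans until the next scheduled visit, about Day 630 (Month 21), some 90 days past target. One who attended keeps only a week.

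**3. What happens to a repeat at visit + 15 days (Day 555 for a visit on Day 540).** It lies past the cut-off of Day 547, so Table 2 excludes it and Table 6 labels it Month 30. If no other usable Month 18 scan exists and no activity was shown earlier, the participant leaves the mFAS. If the repeat shows a new lesion, that lesion is not counted. In the final analysis, continuous variables use the scan closest to Day 900 (SAP 2.4.1.1), so the repeat serves as a Month 30 value mainly when no real Month 30 scan exists. It would then stand 345 days before target (900 − 555).

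**4. Size.** The documents give no repeat rate, so the number lost, k, is an assumption: 2, 5 or 10 of 100 evaluable participants, with a true NEDA-3 of 80/100. The two mFAS columns are bounding cases.

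| k lost | mFAS if all lost were responders | mFAS if all lost were failures seen only on the late scan | Non-response imputation if all lost were responders |
|---|---|---|---|
| 2 | 78/98 = 79.6% | 80/98 = 81.6% | 78% |
| 5 | 75/95 = 78.9% | 80/95 = 84.2% | 75% |
| 10 | 70/90 = 77.8% | 80/90 = 88.9% | 70% |

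With the proportion held at 80%, the exact half-width goes from 8.26% (80/100) to 8.72% (72/90). The same assumed 2% to 10% of 50 healthy controls is 1 to 5 missing Month 18 brain-volume values.

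**5. The steroid rule.** The first permitted scan is 31 days after the course ends. It falls past visit + 7 only if the course ends fewer than 24 days before the visit. Protocol 6.2.3 describes courses of 3 to 5 days, so one ending 23 days before the visit starts at most 27 days before it. A scan scheduled on the visit day is then within 30 days of starting steroids, and the scan-first rule applies. That scan, at about Day 513 (540 − 27), falls inside the window that opens on Day 451.

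**The case against.** **The cut-off matches the protocol's MRI window.** The protocol asks for each scan within 7 days of the visit, and Table 2 uses the same 7 days. This stands: a reader might infer that the SAP discards scans that fully comply with the protocol, or contradicts it outright. The documents support only that the fate of a late repeat was not provided for.

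**Repeats need not be late.** A reader might assume that a repeat usually falls after visit + 7 days. No turnaround time is given, the first scan may precede the visit by up to 7 days, and quality is assessed on receipt. A repeat done by visit + 7 is kept. The claim covers only those done later.

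**Steroid delay.** A reader might add scans postponed after steroids. An annualized relapse rate of 0.11 (protocol 1.1) over an assumed 35-day span in 118 participants gives 0.11 × 35/365 × 118 = 1.2 relapses. But that rate counts confirmed relapses, which are already NEDA-3 failures and stay in the mFAS. Step 5 shows that the scan-first rule otherwise yields a scan inside the window, except where the scan was scheduled several days after the visit. This route is negligible for NEDA-3 when the protocol is followed.

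**The endpoint definition seems to admit the scan.** SAP 2.5.1 defines MRI activity on any scan after Month 6, scheduled or not. That does not rescue a late repeat, because Table 2 fixes which data enter the primary analysis.

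**The asymmetry comes from the mFAS.** True: any missing Month 18 MRI has the same effect. The cut-off adds avoidable cases.

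**Other analyses cover it.** The observed-case analysis requires completed Month 6 and Month 18 visits rather than a Month 18 scan, and all data are listed. Neither brings the late scan into the Month 18 result.

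**Conclusion.** The gap is real and follows from Table 2 and Table 6 applied as written. It is separate from the fact that SAP 2.13 states a still earlier cut-off, the visit date itself. It affects participants who completed the Month 18 visit and whose requested repeat came more than 7 days after it. The consequences for the primary endpoint further require that no other usable Month 18 scan exists.

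Its size is unknown and probably small. The half-width effect is under half a percentage point even with 10 of 100 lost. The point estimate could move further if the lost scans differ in outcome, but the table's extremes assume that every lost participant had the same outcome, and the 2 to 10 range is itself an assumption. The text does not support a general claim that late repeats become Month 30 data, since a true Month 30 scan would normally displace them. This is a cheap improvement, not a threat to the primary analysis.

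**What to change.** In SAP Tables 2 and 6, count a repeat of the Month 18 scan requested by the reading centre as Month 18 if done within a fixed limit, and exclude it from the Month 30 window. Set the limit before database lock and without reference to scan results. The roughly 90 days already allowed to participants who missed the Month 18 visit is a natural ceiling, and a shorter limit would do. Keep visit + 7 days for all other data.

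The cost is SAP wording, with no new procedures. The downside should be stated: a few participants would have a longer MRI interval, so lesions arising shortly after Month 18 could count as Month 6 to 18 activity while relapse and EDSS data stop at visit + 7. For those not entering the extension, whose end-of-study visit is at Month 18 (protocol 9.3), such a scan may also fall after treatment has ended. Footnote these participants, give their scan dates, and show NEDA-3 with and without them.

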### 2.5.1 Primary endpoint(s)

The primary endpoint is NEDA-3 (relapse-free, 3-month clinical disability progression-free, MRI activity-free) in Months 6 to 18 (yes/no). The 3 components of the primary endpoint are defined as follows:

- Relapse-free is defined as no confirmed relapses. Partial relapse start and end dates will be imputed as outlined in [Section 5.1.3.3](#). Criteria for the linking/combining of individual relapses is outlined in [Section 5.1.3.4](#).
- 3-month clinical disability progression-free is defined as no clinical disability progression as measured by EDSS (global assessment scale), where 3-month confirmed clinical disability progression is defined as an increase from Month 6 in EDSS (global assessment scale) sustained for at least 3 months. That is, after a scheduled or unscheduled visit at which the participant fulfills the clinical disability progression criteria as outlined in [Table 7](#), all EDSS assessments (scheduled or unscheduled) need to also fulfill the clinical disability progression criteria until the progression can be confirmed at the first scheduled visit that occurs in the absence of relapse (confirmed or unconfirmed) 3 months after the onset of the progression, or later. If a participant fulfills the clinical disability progression criteria based on the single EDSS assessment at Month 18, it will be considered a confirmed clinical disability progression (sustainment for at least 3 months will not be required). If a participant dies due to MS (i.e., EDSS = 10 at any time), it will be considered a confirmed clinical disability progression regardless of the Month 6 EDSS or change in EDSS.

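### SAP Table 2's fallback cut-off has no end date, so in a rare case a scan or EDSS as late as Month 30 can be analysed as Month 18 and enter NEDA-3

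*SAP*

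**What the plan says.** SAP 2.5.1 defines the endpoint by period: "The primary endpoint is NEDA-3 (relapse-free, 3-month clinical disability progression-free, MRI activity-free) in Months 6 to 18 (yes/no". SAP 2.1 fixes the data span: "The primary analysis will be based on Month 18 data, i.e., all data up to and including Month 18". SAP 2.1.1 repeats this under the cut-off heading, and SAP 2.13 limits the outputs to data up to each participant's Month 18 visit date.

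Table 2 in SAP 2.1.1 then gives the cut-off by scenario:

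- Month 18 completed: "All available data up to the date of the Month 18 visit + 7 days (inclusive".
- Month 18 not completed, still in the study: "All available data up to the date of the next scheduled visit (including home visit) after Month 18 (exclusive".
- The same participant, with the following visit also not completed: "If the next scheduled visit after Month 18 has not been completed, all available data is used".

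The text above the table adds "Note that visits are assumed to be nominal visits", so the visit after Month 18 is Month 21 (Day 630). Protocol Table 8-1, footnote 6, makes Months 21, 24 and 27 remote contacts.

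The notes to the visit-window tables in SAP 2.4.1.1 say "Cut-off day is the study day of the Month 18 interim analysis data cut-off". In Tables 3, 4 and 6 the Month 18 window starts at Day 451, and in Table 5 at Day 2. In all four it ends at the cut-off day, and Month 30 starts one day later.

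**The concern.** The fallback is the only line for a participant still in the study that carries no date. If Month 21 was skipped but a later visit was attended, no cut-off day exists, and the Month 18 windows that depend on it stay open. An assessment made up to a year after Month 18 could then be labelled Month 18.

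The case is not excluded by design. Protocol Section 8 says that missed visits should not lead to automatic discontinuation. SAP 5.6, scenario 3, provides for extension dosing without a completed Month 18 visit. The analysis runs only after the last participant's Month 18 visit, so early enrollees may already have extension data.

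At stake is a primary endpoint whose observation period could differ between participants because of an open-ended data rule, and a later value summarised under the Month 18 label.

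**Working it through.** **Day limits under each line of Table 2** (visit days and ±3-day windows from protocol Table 8-1)

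| Scenario | Last day of data |
|---|---|
| Month 18 completed | 540 + 7 = 547; at the latest 540 + 3 + 7 = 550 |
| Month 18 missed, Month 21 done | 630 − 1 = 629; range 626 to 632 |
| Both missed, later visit attended | no limit; the Month 30 visit is Day 900 |

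**Does another rule stop the late assessment?**

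- *MRI window.* With no cut-off day, a Day 900 scan falls in the Month 18 window of Table 6 and never reaches the Month 30 window.
- *MRI component.* SAP 2.5.1 counts lesions on any scan, scheduled or not, after Month 6 and gives no end day.
- *EDSS.* Table 3 has the same open window. SAP 2.5.1 also accepts progression on the single Month 18 EDSS as confirmed, without three months of sustainment. A Day 900 EDSS mapped to Month 18 could therefore count as confirmed progression.
- *Analysis set.* The mFAS exclusion for missed assessments in SAP 2.2 applies only to those who completed Month 18. An affected participant stays in the primary analysis.
- *Relapses.* SAP 2.1.1 assigns them to the open-label treatment phase by the same cut-off. However, SAP 2.2, 2.5.1 and 2.5.3 limit relapse to Months 6 to 18, so this route is doubtful.
- *Several values in one window.* For continuous variables SAP 2.4.1.1 takes the value closest to the target day, 540. The late value is used only if nothing closer exists.

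**The plan's own precision, as a yardstick** (SAP 3.1; n = 100)

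- At 80%: 1.96 × √(0.80 × 0.20 / 100) = 7.8%.
- At 85%: 1.96 × √(0.85 × 0.15 / 100) = 7.0%.
- Enrolment: 100 / 0.85 = 117.6, rounded up to 118.

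All three figures reproduce.

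**How many affected participants would change status?** The failure risk is an assumption: 20% and 15% by the completers' limit, matching the 80% and 85% planned for, with a constant hazard.

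- Time from Day 180 to the completers' limit: 547 − 180 = 367 days. To Day 900: 720 days. Ratio: 720 / 367 = 1.96.
- Risk to Day 900 = 1 − (1 − r)^1.96. For r = 20% this is 35.5%; for r = 15% it is 27.3%.
- Only first events in the added time change the classification: 35.5 − 20 = 15.5% and 27.3 − 15 = 12.3% of those affected.
- With 360 days as the base (180 to 540), the ratio is 2: 1 − 0.80² − 0.20 = 16.0% and 1 − 0.85² − 0.15 = 12.8%.

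This gives about 12 to 16%. It treats all three components as exposed; if relapses are held to Month 18, the share is lower.

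**Effect on the estimate.** The documents do not give the number affected; 1 to 5 among 100 is an assumed range. Expected reclassifications run from 1 × 0.123 = 0.1 to 5 × 0.155 = 0.8, so less than 1 percentage point. One actual switch moves 80/100 (exact 95% CI 70.8 to 87.3%) to 79/100 (69.7 to 86.5%).

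**The case against.** The strongest reply is that the sentence means a visit not yet completed at lock. For such a participant there are few later data to admit, and the rule is harmless. SAP 5.6 (scenario 3) and the start of the Month 30 window one day after the cut-off both presuppose a finite cut-off for anyone with extension data. This is probably the intention. The words do not say so, however, and nothing separates a visit not yet due from one that was skipped.

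The case also needs several coincidences: Month 18 missed, participation continued, the remote Month 21 contact skipped, a later return, and those data in hand at lock. Protocol Table 8-1 places extension consent at Month 18 and dispensing at Months 18 and 21, and protocol 6.6.1 calls for review when compliance falls below 80%. This stands, and it keeps the point small.

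A reader might infer that a relapse at, say, Month 26 makes the participant a NEDA-3 failure. The documents do not support that with any confidence: Table 2 is a data cut-off, and the endpoint text separately limits relapses to Months 6 to 18. SAP 2.2 and 2.5.3 also describe MRI activity as running through Month 18. That is weaker protection, because the tables themselves let Month 18 run to the cut-off day.

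A reader might also infer that Month 30 values are generally reported as Month 18 values. They are not: for continuous variables the closest-to-target rule applies first.

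Finally, the supplementary observed-case analysis in SAP 2.5.6 requires a completed Month 18 visit, so it leaves out every affected participant. It gives a check on the primary result but does not repair the primary rule.

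**Conclusion.** The point holds as a narrow defect. Read literally, the fallback removes the upper limit for a participant who missed both Month 18 and the following nominal visit and later returned. A late EDSS or MRI can then be analysed as Month 18 and can enter NEDA-3. This conflicts with the stated span: "the primary analysis will be based on Month 18 data (i.e., all data up to and including Month 18".

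It would be tempting to say that every affected participant is misclassified. That is not so. Those who failed by Month 18 are failures either way, and those with no later activity are unchanged. Only first activity after Month 18 matters, about 12 to 16% of the affected under the assumed 15 to 20% risk and constant hazard. Compared with classifying the same participants on data up to Month 18, the added time can only add failures, so any bias lowers the NEDA-3 proportion. With an assumed 1 to 5 affected, the expected shift is below 1 point, against a planned half-width of 7.0 to 7.8 points. The main conclusion of the trial is not at risk. The rule is still worth closing before lock, so that no individual cut-off has to be chosen once the data are visible.

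**What to change.** Replace the fallback sentence in SAP Table 2 with a fixed limit, for example: *Where the following nominal visit was skipped or is not yet due, data are cut at Study Day 629 (one day before planned Month 21), or at the last available date if earlier.* Apply the same cap to the cut-off day in SAP Tables 3 to 6, so that a Day 900 assessment falls in Month 30.

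Day 629 gives a skipped Month 21 the same nominal limit as an attended one, but it still admits 629 − 540 = 89 days after Day 540. For NEDA-3 and its components, therefore, also state in SAP 2.5.1 that only events and assessments up to the completers' limit (one fixed day between 547 and 550) count as within Months 6 to 18. Bring the data-span statements in SAP 2.1, 2.1.1 and 2.13 into line with this.

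The cost is a few sentences in the SAP and a date cap in the programs. No new data are needed.
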